Official Title: Newer Direct-Acting Anti-Viral Agents as Sole Therapy of
Porphyria Cutanea Tarda in Subjects With Chronic Hepatitis C

NCT03118674

IRB-Approved Date: 5/5/2020

Rare Diseases Clinical Research Network

Porphyrias Consortium

Newer Direct-Acting Anti-Viral Agents as Sole Therapy of Porphyria Cutanea Tarda in Subjects with Chronic Hepatitis C

This protocol is for research purposes only, and should not be copied, redistributed or used for any other purpose. The procedures in this protocol are intended only for use by the Porphyrias Consortium investigators in carefully controlled settings. The Study Chair of this study should be consulted before using or attempting any procedure in this protocol.

Study Chair:

[name] MD

Professor of Medicine, Molecular Medicine & Translational Science
Wake Forest School of Medicine

[name]
[name]
[contact]
[contact]

Email: [contact]

Table of Contents

1. Protocol Synopsis	3
1.1 Overview	5
2. Specific Aims (Hypothesis and Objectives)	6
3. Background	6
4. Study Design and Methods	7
4.1 Inclusion Criteria	9
4.2 Exclusion Criteria	9
4.3 Recruitment of Participants	10
4.4 Retention Strategies	11
4.5 Data Elements	11
4.6 Study Procedures	12
4.7 Schedule of Events	15
4.8 Investigational Product	16
5.0 Data and Safety Monitoring Plan	16
5.1 Study Oversight	17
5.2 Definitions and Standards	17
5.3 Expected/Known Risks/Discomforts/Adverse Events Associated with Study Intervention and Procedures: Definition of Expected Adverse Events	17
5.4 Reporting Timeline	19
5.5 RDCRN DMCC Adverse Event Monitoring System	20
5.6 Study Discontinuation	20
5.7 Subject Discontinuation	21
5.8 Data Quality and Monitoring Measures	21
5.9 Quality Control: Study Related Procedures	21
6. Statistical Considerations	22
7. Data Management	24
7.1 Registration	24
7.2 Data Entry	25
8. Human Subjects	25
8.1 GCP Statement	25
8.2 Benefits	25
8.3 Risks	25
8.4 Written Informed Consent	26
8.5 Process of Consent	26
9. References	28
10. Appendices	29
I. Sample Processing Instructions	29

1. Protocol Synopsis

Interventional Synopsis

Protocol Number:	7210
Protocol Title:	Newer Direct-Acting Anti-Viral Agents as Sole Therapy of Porphyria Cutanea Tarda in Subjects with Chronic Hepatitis C
Study Chair:	[name]
Statistician:	[name]; [name], MS
Consortium:	Porphyrias Consortium
Activation Date:	04AUG2017
Current Status:	Enrolling
Sample Size:	49
Target Enrollment Period:	3 years

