Study Design:	Interventional, one arm, open label non-inferiority
Primary Study Objective:	To assess whether Harvoni alone is an effective therapy of active PCT (measured as resolution of active PCT by 7 months) in patients with Chronic Hepatitis C (CHC).
Secondary Study Objective(s):	To assess time to resolution of active PCT after initiation of treatment with Harvoni; To assess time course of normalization of urinary porphyrin profiles; To assess cure of chronic hepatitis c
Study Population and Main Eligibility/ Exclusion Criteria:	
Inclusion Criteria:
 
 1. Willing and able to give informed consent 2. ≥18 years of age 3. Symptoms and signs consistent with PCT and well documented biochemical diagnosis (urinary total porphyrin excretion > 500 mcg/g creatinine with HPLC pattern typical of PCT—predominance of 8- and 7-carboxyl porphyrins [>50% of total]) 4. Clinical diagnosis of PCT established by a study PI 5. Chronic hepatitis C: HCV RNA positive and quantifiable in serum detected within 90 days of enrollment, and documented HCV genotypes 1,4, 5, or 6 for which Harvoni is an approved therapy. 6. Women of child-bearing potential must be willing to avoid pregnancy and use an accepted and effective contraceptive method during treatment. 
Exclusion Criteria:
 
 1. Women who are pregnant or who are breast-feeding 2. Patients who have already started treatment of PCT with phlebotomy or low dose hydroxychloroquine or chloroquine, or who have been in such treatment in the past 30 days 3. Patients who have already started another treatment regimen for CHC, or who have taken such treatment in the past 30 days 4. HIV infection with CD4 counts at baseline less than 350/µL or with evidence of any active AIDS-defining illnesses 5. Ongoing active alcohol abuse, defined as a history of drinking more than 25 drinks of alcohol per week during most weeks in the prior 4 months (History of prior, but not current alcohol abuse will NOT be grounds for exclusion because we seek to treat subjects with PCT and CHC of the type typically seen in clinical practice)

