	
 6. Any ongoing active IV drug use 7. Patients who are taking amiodarone or who have taken amiodarone within 60 days prior to enrollment 8. Patients who are taking, or within the prior 28 days have taken, rifampicin or St John's wort (Hypericum perforatum), both of which are P-gp inducers, which may significantly reduce the drug levels and therapeutic effects of Harvoni 9. Uncontrolled diabetes (Hgb A1c >9.5% within 60 days prior to enrollment) 10. Chronic hepatitis B 11. Autoimmune hepatic liver injury—autoimmune hepatitis, primary biliary cholangitis/sclerosing cholangitis or overlap syndrome 12. Alcoholic hepatitis 13. Other metabolic disorders of the liver, e.g. Alpha 1 antitrypsin deficiency with ZZ Pi type, Wilson's disease 14. Prior known or suspected drug-induced liver injury within 6 months of enrollment 15. Known or suspected hepatocellular carcinoma 16. On liver transplant list, or current MELD >12 17. History of liver transplant 18. Estimated GFR (creatinine clearance) <30 mL/min (per Sofosbuvir being cleared by the kidney) 19. Serum ALT or AST >10x upper limit of normal 20. Serum bilirubin >2 mg/dL (excluding patients with known or suspected Gilbert's syndrome) 21. Any other comorbid condition, which in the opinion of the investigator precludes participation 22. Incarcerated individuals
Treatment (if applicable)	
Agent-	Harvoni—ledipasvir, 90 mg + sofosbuvir, 400 mg
Dosage, schedule, route of administration-	1 tablet per day, oral, taken with or without food. 8 weeks for patients without cirrhosis, not previously treated with HCV GT1 and HCV RNA < 6 million IU/mL; 12 weeks for patients without cirrhosis; 24 weeks for patients with compensated cirrhosis.
Safety Issues-	The drug is well-tolerated and highly effective for cure of HCV
Primary Outcome Measures:	The primary endpoint will be resolution of active PCT, defined as normalization of plasma porphyrins (less than 0.9 mcg/dL) by 7 months after start of therapy.

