Aim: To assess whether Harvoni alone is an effective and durable therapy of active PCT in patients with CHC due to any genotype for which Harvoni is approved for treatment, currently genotypes 1, 4, 5, or 6. Genotype 1 HCV accounts for ~ 75% of chronic hepatitis C infections in the USA. Genotype 4 is common in Egypt; rare in the USA, but it does occur. Our goal is to be as inclusive as possible and to test effects of Harvoni treatment in real-world situations. We will test whether Harvoni treatment is non-inferior to previously published remission times of other standard treatments of PCT (low dose hydroxychloroquine or phlebotomy therapy) (Singal et al, 2012).

Hypothesis: Treatment of PCT associated with CHC with Harvoni is as effective and as durable as published data on the current standard treatments of iron reduction by phlebotomies or low dose hydroxychloroquine.

3. Background:

CHC is a well-known risk factor for PCT. Other risk factors include hepatic iron overload, often related to mutations of *HFE* associated with hereditary hemochromatosis, excess alcohol use, estrogen therapy, and HIV infection ([name] et al, 1998, 2013; Egger et al, 2002; Besur et al, 2014).

The standard of care therapy for PCT has been iron reduction by therapeutic phlebotomy, which has been effective in nearly all subjects, regardless of underlying major risk factors (Besur et al, 2014; [name] et al, 1998, 2013). Based upon more recent results, low-dose therapy with 4-aminoquinolones, (chloroquine and/or hydroxychloroquine), also has become a standard therapy, as has a combination of iron reduction and one of these agents (Stölzel et al, 2009; Singal et al, 2012; [name], unpublished). However, it has been found that decreases in measures of iron status following chloroquine therapy did not occur in subjects with *HFE* mutations and that C282Y +/- subjects did not respond very well to chloroquine (Stölzel et al, 2003). In addition, the use of 4-aminoquinolones, as against phlebotomy therapy, may be associated with earlier recurrence of active PCT after a course of therapy than after a course of iron reduction and maintenance of an iron-reduced state (Stölzel et al, 2003, 2009; & [name], unpublished observations). This led to the recommendation that, for those with *HFE*-linked hemochromatosis, therapeutic phlebotomy should remain the treatment of first choice (Stölzel et al, 2003).

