4.2 Exclusion Criteria

1. Women who are pregnant or who are breast-feeding
2. Patients who have already started treatment of PCT with phlebotomy or low dose hydroxychloroquine or chloroquine, or who have been in such treatment in the past 30 days
3. Patients who have already started another treatment regimen for CHC, or who have taken such treatment in the past 30 days
4. HIV infection with CD4 counts at baseline less than 350/ μ L or with evidence of any active AIDS-defining illnesses
5. Ongoing active alcohol abuse, defined as a history of drinking more than 25 drinks of alcohol per week during most weeks in the prior 4 months (History of prior, but not current alcohol abuse will NOT be grounds for exclusion because we seek to treat subjects with PCT and CHC of the type typically seen in clinical practice)
6. Any ongoing active IV drug use
7. Patients who are taking Amiodarone or who have taken Amiodarone within 60 days prior to enrollment
8. Patients who are taking, or within the prior 28 days have taken, rifampicin or St John's wort (*Hypericum perforatum*), both of which are P-gp inducers, which may significantly reduce the drug levels and therapeutic effects of Harvoni
9. Uncontrolled diabetes (Hgb A1c $>9.5\%$ within 60 days prior to enrollment)
10. Chronic hepatitis B
11. Autoimmune hepatic liver injury—autoimmune hepatitis, primary biliary cholangitis/sclerosing cholangitis or overlap syndrome
12. Alcoholic hepatitis

13. Other metabolic disorders of the liver, e.g. Alpha 1 antitrypsin deficiency with ZZ Pi type, Wilson's disease
14. Prior known or suspected drug-induced liver injury within 6 months of enrollment
15. Known or suspected hepatocellular carcinoma
16. On liver transplant list, or current MELD >12
17. History of liver transplant
18. Estimated GFR (creatinine clearance) <30 mL/min (per Sofosbuvir being cleared by the kidney)
19. Serum ALT or AST >10x upper limit of normal
20. Serum bilirubin >2 mg/dL (excluding patients with known or suspected Gilbert's syndrome)
21. Any other comorbid condition, which in the opinion of the investigator precludes participation
22. Incarcerated individuals

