The therapy will be Harvoni at the usual dose (90 mg of ledipasvir and 400 mg of sofosbuvir) and duration for CHC therapy. One tablet taken daily for 8 weeks for patients without cirrhosis, not previously treated with HCV GT1 and HCV RNA < 6 million IU/mL; 12 or 24 weeks, duration to be determined based upon clinical features and prior treatment experience. 8 or 12 weeks for subjects with or without cirrhosis, not previously treated with anti-virals for CHC, and 24 weeks for subjects with cirrhosis who were previously treated with anti-virals for CHC without having achieved SVR. During the first year study visits will be monthly, and this includes the treatment period of either 12 or 24 weeks. To assess cure of HCV infection, repeated HCV RNA levels at 3, 6, and 12 months after end of Harvoni therapy will be done, as well as annually thereafter. Evaluation by a hepatologist at follow up visits will be as needed, determined by the screening lab test results and by clinical and lab findings at follow-up visits.

Lab measures to be checked monthly during therapy will include CBC, CMP, plasma total porphyrins, urinary total porphyrins (with HPLC), and levels of HCV RNA in serum by quantitative PCR (Section 4.7 Schedule of Events).

Porphyrin specific lab tests will be performed at the UTMB Porphyria Laboratory; all other labs will be performed at Covance Laboratories.

Subjects who have their treatment discontinued for any reason will continue to be followed until the end of the study, including longer-term follow up visits, unless they withdraw consent. If a subject becomes pregnant during the study Harvoni will be discontinued. The outcome of the pregnancy will not be followed as part of this study. Pregnancy during the study should be reported as an SAE.

Longer-Term Follow-up:

12 months after beginning treatment, subjects will be asked to return every four months for one year, with repeat of interval history and physical examination (especially to reassess the status of cutaneous lesions of PCT) and the above studies.

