4.7 Schedule of Events

	Screening (-30 to -1 Days)	Day 0	Day 30	Day 60	Day 90	Day 120	Day 150	Day 180	Day 210	Day 240	Day 270	Day 300	Day 330	Day 360	Day 480	Day 600	Day 720
			(Window +/- 7 days)														
			M1	M2	M3	M4	M5	M6	M7	M8	M9	M10	M11	M12	M16	M20	M24
Consent	X																
Complete Medical History	X																
Interval Medical History		X	X	X	X	X	X	X	X	X	X	X	X	X	X	X	X
Physical Examination	X	X			X			X			X			X	X	X	X
Skin Assessment (including pictures)	X	X	X	X	X	X	X	X	X	X	X	X	X	X	X	X	X
Alcohol & Tobacco use questionnaires	X																
Adverse Event/SAE Review														Each visit			
Urine Pregnancy	X																
Anti-HCV antibodies	X																
PTT	X																
Hepatitis B Surface Antigen	X																
HIV-1/HIV-2 Antibodies	X																
Serum Ferritin	X																
Serum iron and TIBC	X																
Complete Metabolic Panel\$	X	X	X	X	X	X	X	X	X	X	X	X	X	X	X	X	X
INR**	X																
HbA1c	X																
Erythrocyte UROD enzyme activity*	X																
UROD mutation analysis*	X																
HFE genetic testing*	X																
Hematology with Differential#	X	X	X	X	X	[X]*	[X]*	X	X	X	X	X	X	X	X	X	X
HCV RNA	X	X				[X]*	[X]*	[X]									
Plasma Total Porphyrins	X	X	X	X	X	X	X	X	X	X	X	X	X	X	X	X	X
Spot Urine ALA, PBG, Total Porphyrins	X	X	X	X	X	X	X	X	X	X	X	X	X	X	X	X	X
Fibroscan (if available at institution)	X														X		X
Dispense Study Drug [€]		X	X	X	X	X	X	X	X								

Hematology (complete blood count): white blood cell count (WBC), red blood cell count (RBC), hemoglobin, hematocrit, platelet count

\$Comprehensive metabolic panel: sodium, potassium, chloride, carbon dioxide, calcium, BUN, creatinine, glucose, and liver panel, including total protein, albumin, total bilirubin (TBR), alanine aminotransferase (ALT), aspartate aminotransferase (AST), alkaline phosphatase (AP)

*If not previously done

**INR (if not done within 4 months of screening)

[€]Drug is only to be dispensed at months 2-6 if additional therapy is warranted

[X]* Samples at these time points will be obtained only in subjects with cirrhosis who 24 weeks of Harvoni therapy is indicated; [X] Samples at these time points will be obtained 3, 6, and 12 months after the end of Harvoni treatment, and annually till end of study or EOT

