Worsening PCT symptoms: PCT is a rare disease and no standard disease severity scale exists. A standardized detailed skin assessment including pictures will be done at each time point in this study. If a subject experience significantly worsening symptoms in the opinion of the investigator that persist for 60 days, HCV therapy will be discontinued under the study and standard of care PCT treatment will be initiated. This length of time may be shortened depending on the severity of the subject’s PCT symptoms. Any patient who experiences worsening PCT symptoms must be discussed by the site PI with the Study Chair prior to discontinuing Harvoni.

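### The primary endpoint sets no condition on other PCT treatment, so a patient switched from Harvoni to standard PCT treatment who normalises by Month 7 may be scored a Harvoni success

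*Combined protocol and SAP*

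**What the plan says.** **The question.** The title describes the antivirals "as Sole Therapy of Porphyria Cutanea Tarda in Subjects With Chronic Hepatitis C". The synopsis objective is "To assess whether Harvoni alone is an effective therapy of active PCT (measured as resolution of active PCT by 7 months", and Section 2 repeats the idea: "To assess whether Harvoni alone is an effective and durable therapy of active PCT in patients with CHC".

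**The endpoint.** The synopsis and Section 6 give resolution of active PCT, "defined as normalization of plasma porphyrins (less than 0.9 mcg/dL) by 7 months after start of therapy". Neither mentions other PCT treatment.

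**Other PCT treatment.** It is restricted at entry. Exclusion 2 in Section 4.2 covers "Patients who have already started treatment of PCT with phlebotomy or low dose hydroxychloroquine or chloroquine", as well as such treatment in the past 30 days. After entry, Section 5.3 (worsening PCT symptoms) provides that after significant worsening lasting 60 days, a period that may be shortened, "HCV therapy will be discontinued under the study and standard of care PCT treatment will be initiated". The site investigator must first discuss the case with the Study Chair.

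**Follow-up after stopping.** Section 4.6 says "Subjects who have their treatment discontinued for any reason will continue to be followed until the end of the study", unless they withdraw consent. The Section 4.7 row "Plasma Total Porphyrins" is marked at every monthly visit through Month 12.

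**Data use after stopping.** Section 5.7 announces an intent-to-treat approach and says that data acquired before termination enter the primary analysis. It lists the Section 5.3 worsening under withdrawal by the investigator and asks for a final study visit. It does not say what happens to later data.

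**Failure rule.** Section 6 scores a patient as a failure when data are missing because of severity of illness. Other missing outcomes are multiply imputed, using plasma porphyrins measured up to 6 months.

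**The concern.** Sections 5.3, 4.6 and 6, taken in turn, allow a response to phlebotomy or (hydroxy)chloroquine to be credited to Harvoni. The severity-of-illness rule does not prevent this, because the Month 7 value is observed. The best-case and worst-case sensitivity analyses in Section 6 do not reach it either, for the same reason.

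The design makes this matter more than it would in a randomised trial. There is no control arm to offset rescue, and the 50% performance goal was itself built from phlebotomy and hydroxychloroquine results. Any miscredited response pushes towards a claim of non-inferiority.

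Section 5.7 adds a second problem: under its other reading the same patient gets a different score. Settling that after outcomes are known would leave the choice open to the result.

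**Working it through.** **1. One patient, several scores.** Take a patient who worsens on Harvoni, starts standard PCT treatment at about month 3 and has a plasma value below 0.9 mcg/dL at Month 7.

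| Reading | Month 7 value | Score |
|---|---|---|
| Section 4.6 (followed up) with the Section 6 endpoint | observed, normal | success |
| Section 5.7 as leaving the study, missing because of severity | not used | failure |
| Section 5.7 as leaving the study, missing for another reason | not used | imputed |

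No sentence chooses between these rows.

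**2. The plan's own figures.** Inputs from Section 6: n = 49, success at 26 or more, null 0.40, assumed true rate 0.58, one-sided 0.05. By the exact binomial:
- Power: P(X ≥ 26 | 0.58) = 0.8015. The stated 80.2% reproduces.
- Type I error: P(X ≥ 26 | 0.40) = 0.0439. Table 3 prints 0.0434, a small difference that does not affect the rule.
- Exact one-sided 95% lower bound: 0.3847 at 25/49 (fails) and 0.4043 at 26/49 (passes).

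**3. How many switched patients could normalise in time (assumed).** Section 6 gives a median of 6 to 7 months on standard treatment but no response curve. For a switch at month t, median m and Weibull shape k, the share normalising by Month 7 is f = 1 − 2^(−((7 − t)/m)^k). The extremes taken are t = 4, m = 7 and t = 2, m = 6.

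| Shape k | f, low | f, high |
|---|---|---|
| 1 (exponential) | 0.257 | 0.439 |
| 2 | 0.120 | 0.382 |
| 3 (delayed response) | 0.053 | 0.330 |

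A working range of 5% to 40% covers nearly all of this.

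**4. Effect on type I error.** Let s be the share of all patients who switch and would have failed on Harvoni alone. At a true Harvoni-alone rate of 0.40 the credited rate is 0.40 + s × f. For example, s = 0.05 and f = 0.40 give 0.42, and P(X ≥ 26 | 0.42) = 0.0780.

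| s | patients of 49 (49 × s) | f = 0.05 | f = 0.25 | f = 0.40 |
|---|---|---|---|---|
| 0 | 0 | 0.0439 | 0.0439 | 0.0439 |
| 1% | 0.49 | 0.0445 | 0.0473 | 0.0495 |
| 2% | 0.98 | 0.0452 | 0.0510 | 0.0557 |
| 5% | 2.45 | 0.0473 | 0.0634 | 0.0780 |

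The rejection probability reaches 0.05 at a credited rate of 0.4043. The break-even share is therefore s = 0.0043/f, which is 1.1% at f = 0.40 and 8.6% at f = 0.05 (using the unrounded 0.00432).

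**5. How narrow the written route is.** Section 4.8 expects most subjects to take 12 weeks (84 days). A full 60-day worsening must begin by day 84 − 60 = 24 to be complete while on drug. In an 8-week course (56 days) it cannot be complete on drug unless the period is shortened, which Section 5.3 allows.

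**6. Cost of scoring switches as failures.** If 1% of all patients switch but would have resolved on Harvoni alone, the success rate at a true 0.58 falls to 0.57, and P(X ≥ 26 | 0.57) = 0.7593.

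**The case against.** The strongest reply is that Section 5.7 already deals with this event. It names the worsening as a ground for withdrawal, and its statement about data before termination explains what intent to treat means here. On that reading the post-switch value is not used, and the patient is probably a failure for severity of illness. This is a fair reading, and it rules out saying that such a patient is certainly scored a success. It does not close the gap. Section 5.7 never excludes later data, and Section 4.6 says that follow-up continues after discontinuation for any reason.

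The second reply is that switches will be rare and that every size above rests on assumed shares. That also stands. The median in Section 6 comes from patients treated with phlebotomy or hydroxychloroquine in general, not from patients selected for worsening on an antiviral. Still, Section 3 itself cites reports of antiviral therapy precipitating or worsening PCT, so a switch is not a purely theoretical event.

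A reader might infer serious inflation of type I error. With s = 10%, about five patients, the same formula gives 5.1% to 12.9% for f of 5% to 40%. Nothing in the documents suggests so many switches, and the narrow route argues against it. A reader might also take the step from 25 to 26 successes as proof of the defect. Any binary rule has such a step; it shows only that one misclassified patient could matter.

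Third, counting switches as failures is a choice and it costs some power. That is true, and the cost is stated under the fix.

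**Conclusion.** The gap is real but conditional. As written, a switched patient who normalises by Month 7 may be credited to Harvoni, and Sections 4.6, 5.7 and 6 give the same patient different scores. The documents do not support the stronger statement that this will happen, or that the trial's conclusion is unsafe.

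The effect is nil with no switches and probably small with few. For f of 5% to 40%, type I error is 4.5% to 5.0% at s = 1%, 4.5% to 5.6% at s = 2% and 4.7% to 7.8% at s = 5%, against 4.4% with no switches. These figures rest on assumed values of s and f. Severity is low to moderate and confidence is moderate; the change is a cheap improvement.

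**What to change.** In Section 6, before outcome data are examined:
- State that a patient who starts phlebotomy, hydroxychloroquine or chloroquine for PCT before Month 7 and before meeting the primary endpoint is counted as resolution not achieved, whether later values are observed or missing.
- State whether resolution means the first value below 0.9 mcg/dL by Month 7 or status at Month 7. If it is status at Month 7, any such start before the Month 7 assessment counts as not achieved.
- Leave plasma values after such a start out of the imputation model.
- Report the result regardless of switch as a sensitivity analysis.

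Align Sections 4.6 and 5.7 on whether follow-up continues after such a stop and how later data are used. Record the start date and reason for the other PCT treatment if the case report form, which is not in the documents, does not already hold them. Applying the same convention to the descriptive Kaplan-Meier endpoints is optional.

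The cost is wording and perhaps two data fields, with no extra patients or visits. With switches scored as failures, n = 49 and the threshold of 26 stand, and type I error at a true Harvoni-alone rate of 0.40 stays at 4.4%. The downside is a possibly lower success rate: if 1% of patients switch but would have resolved on Harvoni alone, power at 58% falls from 80.2% to 75.9%. No change to the clinical switching rule is proposed.
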